Study Population. Our clinical population will be men and women (N=5 to 7) 21-60 years old who are currently living with HIV (under antiretroviral therapy for 5+ years with a suppressed viral load).

Recruitment strategy. Co-I [name] has extensive experience in HIV patient recruitment and will oversee the recruitment team, during the recruitment phase, as well as the safety monitoring. Five PLWH (men and women) will be primarily recruited from The SHARC Registry (IRB# 201400073), a UF-IRB-approved registry of over 600 HIV patients who have agreed to be contacted about future research. Written informed consent will be obtained, and blood will be collected at the UF CTRB clinical research center. Inclusion criteria are: ability to read English and provide written consent; willingness to take CBD and to participate in follow up for two months; older than 21 and younger than 60; under antiretroviral therapy for 5+ years and suppressed viral load (CD4 count <350cells/ml); patients must agree to practice acceptable methods of birth control, namely sterilization (female tubal ligation or occlusion, male vasectomy), long-acting reversible contraceptives (intrauterine devices, hormonal implants), short-acting hormonal methods (pill, mini pills, patch, shot, vaginal ring), and condoms.

The main exclusion criterion will be conditions/medications that may impair the immune response (e.g. rheumatoid arthritis, cancer, diabetes chronic infections, CAD, cellulitis, autoimmune diseases such as lupus, sarcoidosis, and all medications they may affect inflammation such as aspirin, steroids, statins);), pregnancy, and current marijuana or CBD use (urine drug screen). Further exclusion criteria will be: excluding subjects taking anti-seizure medicines, with any history of seizure disorder or head trauma, any history of hepatic/liver disease or renal disease, any history of cardiovascular diseases; women who are lactating (in addition to existing exclusion criteria for pregnancy). Co-I [name] (a physician) will review conditions/medications after the initial interview before the patient is enrolled to exclude risks of drug interactions or hepatotoxicity. UF/Shands staff and students will not be considered for enrollment. Presence of chronic pain will not be considered as a necessary condition for enrollment.

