Motivation to study single cells. The molecular and cellular changes underlying the inflammation mitigation caused by CBD-administration are largely unknown, and stand as a major challenge both for understanding its basic biology (e.g., pathways involved, molecular mechanisms) and for the urgent unmet need of reducing the long-term harm chronic inflammation causes in PLWH. Our hypothesis is that CBD alters monocyte migration capacity with MAPK-dependent alterations. We expect this alteration to have

chain-effects based on cellular cross-talk, i.e., that different PBMC cell types (such as Tcells and B-cells) might express specific CBD-induced phenotypes. We hypothesize CBD-alterations to reverberate along the whole immune-modulation system through cellular cross-talk. Given the complexity of the immune response, we deem traditional (bulk) RNA sequencing as insufficient for the task. Population-averaged genomic profiling cannot adequately unravel the inter-cellular regulation in situ. This study will leverage the efficiency of newly available single-cell technologies to create a powerful dataset unveiling the functional properties of thousands of individual cells.

Sample collection and processing. We plan to collect samples from five to seven patients over three time points: baseline (no CBD), and after one and two months of CBD-administration with 5,000 cells sequenced per sample. Five to seven patients (15 to 21 samples) will provide the transcriptomes of 75,000-105,000 single cells, a large dataset for scRNAseq. Immediately after collection, samples will be collected by TBD Lab technician to be processed for scRNAseq at UF ICBR (PBMC scRNAseq experiments are routinely run at ICBR).

Data analysis. During the post-processing period, single-cell reads (count matrices) will be filtered for quality control. Unsupervised clustering will isolate statistically robust populations of similar cells. Clusters will be visualized using Principal Component Analysis (PCA), t-Distributed Stochastic Neighbor Embedding (tSNE), and Uniform Manifold Approximation and Projection (UMAP). The most informative gene expression markers will be identified by a host of non-parametric tests (e.g., the Kolmogorov–Smirnov test), comparing a given cluster against either a nearby cluster or all other clusters. Clusters of cells will be annotated by using their marker genes/pathways⁻ and prior biological knowledge to characterize each sample's cell composition.

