CBD biomarker extraction. We will contrast clusters of the same cell type at baseline (no CBD) and their counterparts after CBD administration. The difference in gene expression, measured in fold change, p-value, and ratio of cell fraction expressing the marker gene, will determine the phenotypic effect of CBD. For each cell type, we expect to extract one or more sets of CBD-specific candidate biomarkers that together will determine a phenotypic CBD per cluster (cell type) signature.

Investigational Product & Dosing Schedule. [name] (Co-I) will oversee CBD dosage and administration.We will source the investigational product from the same batch of our hemp-extract CBD product that is being used in the original protocol under IND 147985, 'Efficacy of a controlled short-term trial of Cannabidiol (CBD) ingestion on reducing symptomatic response and facilitating recovery after induced muscle injury' (Source: SunFlora, Inc, [name])''. SunFlora is a third-party tested hemp-derived product manufacturing company. SunFlora is dedicated to producing high quality hemp-derived products formulated to be safely used by the public and are manufactured in accordance with the Food and Drug Administration (FDA) Current Good Manufacturing Practices (cGMP) for Dietary Supplements, 21 CFR Part 111. Their hemp derived products are assessed multiple times at production process control points throughout the manufacturing process. Dietary ingredients used in the manufacturing process are accompanied by certificates of analyses (CoAs) confirming their identity and specifications. All finished products are tested to ensure they meet specifications prior to being released for distribution. The label and all labeling satisfy FDA requirements found under 21 CFR 101.

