Primary Outcomes: This study takes a single-cell perspective, i.e., we will collect a large number of cells from a small number of patients, and we will measure RNA expression per single cell (not per patient). Note that from the single cell point of view, the number of patients (5-7) is sufficient to derive statistically viable results, as we will collect 5,000 cells from each patient at each time point (total 75,000-105,000 cells). Each cell will be sequence individually to read the RNA expression from a panel of approximately 20,000 genes. Cells will be pooled from all patients, and clustered via unsupervised algorithms into clusters of different cell types (e.g. T cells, B cells, monocytes). Our primary outcomes will be the extraction of gene expression patterns (RNA) from specific immune cell types found in PBMC (e.g., B cells, T cells, monocytes). We will regress these gene markers against the variation in baseline inflammation (C-reactive protein, erythrocyte sedimentation rate, and procalcitonin). After CBD administration to obtain CBD-related biomarkers for inflammation reduction. The difference in gene expression will be measured in fold change, p-value, and ratio of cell fraction expressing the marker gene. These biomarker gene will be unique for each cell type. We expect to extract specific biomarkers for each cell type and understand how CBD alters gene expressions of different immune cells in a different way-overall, we expect the genes of the MAPK signaling pathway (MAPK families play an important role in complex cellular programs like proliferation, differentiation, development, transformation, and apoptosis) to be strongly altered.

Secondary Outcomes. Self-report pain ratings will be used to determine peak pain intensity and pain persistence. The brief pain inventory (BPI) will be used to self-report pain perception. The inventory consists of rating pain on a visual analog scale (VAS). A 10cm line is drawn with 0 (no pain) on the left pole and 10 (worst pain imaginable) on the right pole. The inventory asks participants to rate their level of pain by placing a slash on the line that best represents their current level of pain as well as pain at its worst, best and average over the past 24 hours. The highest worst pain intensity reported during the intervention will be recorded as the peak pain intensity.

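### Pooling cells over patients, with no within-patient contrast, lets a change in who supplies a cluster's cells appear as a CBD fold change

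*Combined protocol and SAP*

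**What the plan says.** All of this is in section 6, Research Plan.

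- **Study Population:** "Our clinical population will be men and women (N=5 to 7) 21-60 years old".
- **Sample collection and processing:** three samples per patient, at "baseline (no CBD), and after one and two months of CBD-administration with 5,000 cells sequenced per sample". The total follows: "Five to seven patients (15 to 21 samples) will provide the transcriptomes of 75,000-105,000 single cells".
- **Data analysis:** the only step named before clustering is a quality-control filter. Clustering "will isolate statistically robust populations of similar cells"; how robustness is judged is not defined. Clusters are then annotated by marker genes and prior knowledge, to describe the cell composition of each sample.
- **Primary Outcomes:** "Cells will be pooled from all patients, and clustered via unsupervised algorithms into clusters of different cell types". The unit of measurement is explicitly the cell and not the patient.
- **CBD biomarker extraction:** "We will contrast clusters of the same cell type at baseline (no CBD) and their counterparts after CBD administration". The effect measures are fold change, p-value and the ratio of the fractions of cells expressing the gene.
- **Safety Monitoring and Stopping Criteria:** a participant may withdraw, be withdrawn or be lost to follow-up. No rule limits the CBD contrast to patients who have both samples.

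No section pairs the contrast within patient, weights patients in the fold change, or asks how many patients contribute to a cluster.

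**The concern.** A fold change over pooled cells weights each patient by the number of cells that patient happens to supply to the cluster. Fixing the number of cells per sample balances patients in the whole pool, but not inside a cluster: one person's monocyte fraction can rise or fall between visits while another's does not. The pooled baseline mean and the pooled on-CBD mean are then averages over differently weighted groups of people. Any standing difference between those people enters the contrast as if it were an effect of CBD.

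This touches the primary outcome directly. The plan's product is a set of CBD signatures by cluster and cell type, meant to support larger studies. Two of its three effect measures, the fold change and the expressing-fraction ratio, are affected in themselves. A better p-value for cells nested in patients would not repair them, so this is separate from the question of treating cells as independent replicates.

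**Working it through.** **1. The plan's own figure.** Cells = patients × visits × cells per sample: 5 × 3 × 5,000 = 75,000 and 7 × 3 × 5,000 = 105,000. Both match the plan. If everyone completes, one patient supplies 15,000 cells: 15,000/75,000 = 20.0% of the pool with five patients, or 15,000/105,000 = 14.3% with seven.

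**2. Fold change from patient mix alone.** Let one patient express a gene at R times the level of the others (set to 1) and supply a share w of the cluster. No patient's expression changes.

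Pooled mean = wR + (1 − w); pooled fold change = mean at follow-up / mean at baseline.

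With R = 2 (assumed):

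- Five patients, share 20% to 30%: means 0.2 × 2 + 0.8 = 1.2 and 0.3 × 2 + 0.7 = 1.3. Fold change 1.3/1.2 = 1.08; log2 = 0.12. If the other four stay equal and unchanged, this needs the patient to supply 0.3 × 4/0.7 = 1.7 times as many cells as before.
- Five patients, share 20% to 50%: 1.5/1.2 = 1.25.
- Five patients, that patient absent at follow-up (20% to 0%): 1.0/1.2 = 0.83; log2 = −0.26.
- Seven patients, that patient absent at follow-up (14.3% to 0%): 1.0/1.143 = 0.88.

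The pooled expressing fraction is a share-weighted average of the same kind. Reading R as the ratio of expressing fractions gives the same ratios.

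**3. The same cases analysed within patient.** Each patient with both samples has a log ratio of 0, so the equally weighted average is 0 and the fold change is 1.00. This includes the case where one patient is absent and drops out of the contrast.

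**4. Null simulation.** There were 1,000 runs per setting, with Poisson counts, about 500 cells per patient per visit in the cluster, no CBD effect and no visit-to-visit change in any patient's expression. The log-scale SDs of patient level and of cluster cell count are assumptions. A pooled Mann-Whitney test stands in for the cell-level test, which the plan does not name for this contrast. The comparator is a one-sample t-test on within-patient log ratios. Rejections at nominal 5%:

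| SD of patient level / of cell count | Pooled, n=5 | Pooled, n=7 | Within-patient, n=5 | Within-patient, n=7 |
|---|---|---|---|---|
| 0.5 / 0 | 5.3% | 5.0% | 3.2% | 4.8% |
| 0 / 0.5 | 4.8% | 3.7% | 6.4% | 5.2% |
| 0.3 / 0.3 | 29% | 33% | 4.1% | 4.7% |
| 0.5 / 0.5 | 61% | 65% | 4.5% | 4.8% |
| 0.7 / 0.5 | 71% | 73% | 4.5% | 3.8% |

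The pooled test fails only when patient level and cluster share both vary, which identifies changed patient mix as the cause. At 0.5 / 0.5 the middle 95% of pooled fold changes ran from 0.76 to 1.28 (n=5) and 0.78 to 1.29 (n=7), with medians of 1.00.

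**The case against.** - **The contrast is by cell type.** The plan compares clusters of the same cell type and names T cells, B cells and monocytes. These should recur in every patient, so a broad cluster made of one person's cells is unlikely. This stands, and it places the risk mainly in fine sub-clusters. Specific Aim 2 looks for a shift within the monocyte population, so such clusters may well arise. A reader might infer a six-way monocyte split, but that comes from the mouse trauma data in the Abstract; no such split is planned for the human samples.
- **Extreme dominance.** A reader might picture one patient supplying 80% of a cluster, about 1.5 effective patients. At cell-type level this does not fit the fixed sample size. If monocytes are 5-30% of 5,000 cells (assumption), a patient gives 250 to 1,500. The largest share for one of five is 1,500/(1,500 + 4 × 250) = 60%, or 1/(0.6² + 4 × 0.1²) = 2.5 effective patients.
- **Noise rather than bias.** If shares vary between visits with no pattern, the pooled log ratio is scattered around zero, as the simulated medians show. A systematic direction needs composition to shift in line with expression level. This stands: the estimate is distorted in a given study, but the documents do not show that it is biased one way.
- **Something did change.** With a fixed number of cells per sample, a changed share among patients seen at both visits usually means that someone's cell composition changed, apart from sampling or clustering noise, and Aim 2 wants to measure that. True, but a change in composition should be reported as such, not as a change in expression. Withdrawal changes the mix with no biological change in anyone.
- **Composition is already described per sample.** That could expose a one-patient cluster, but it is descriptive and does not enter the contrast.

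**Conclusion.** The point holds in a limited form. Followed as written, the plan can turn a change in patient mix into a fold change or a change in expressing fraction with no change in any patient's expression. This is a fault in the stated method and not just missing detail, and it should be corrected before the analysis.

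The size depends on values the documents do not give. With one of five patients at twice the others' level, a moderate shift in share (20% to 30%) gives log2 fold change 0.12, and that patient's absence at follow-up gives fold change 0.83. The 29-73% false-positive rates rest on assumed SDs and a stand-in test; they show the mechanism and do not predict this trial's error rate.

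The documents do not support reading this as a claim that the signatures will describe a single participant, or that the estimate is biased in a known direction. The problem needs patient level and cluster share to vary together, and it is greatest for fine monocyte sub-clusters.

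**What to change.** In section 6, under CBD biomarker extraction and Primary Outcomes:

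1. Define two contrasts, month 1 against baseline and month 2 against baseline. For each, use only patients with both samples.
2. Compute the fold change and the expressing-fraction ratio within each patient, then average over patients on the log scale with equal weight per patient.
3. Report each patient's cell count and share for every cluster at every visit.
4. If a sub-cluster comes mainly from one patient, label it patient-specific and make the expression contrast at the parent cell type.
5. If a sub-cluster is scarce or absent at one visit, analyse it as a within-patient change in cell proportion and do not discard it.

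A fixed minimum of cells per patient at both visits is a tempting alternative. It could remove the very monocyte state that CBD is hypothesised to deplete or induce, and the documents give no basis for a particular threshold. Item 5 keeps that signal.

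The cost is analysis text and programming only: no extra patients, blood or sequencing. Estimates will be somewhat noisier when a patient contributes few cells, and some small sub-clusters will have no expression contrast.

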The main objective of this project will be to identify inflammatory reduction biomarkers linked to MAPK-dependent alterations after CBD administration, as well as other systemic effects on cell signaling pathways. Investigating the role of cell-specific biomarkers describing the molecular response to CBD-administration may open avenues for additional therapeutic strategies that can help reduce the burden of chronic musculoskeletal pain and other pain-related symptoms and comorbidities in people living with HIV (PLWH). The team proposes to study the effects of CBD on inflammation and chronic pain in PLWH by enrolling five persons with HIV who will provide blood samples before and after taking CBD for two months. In the process, the goal will be to establish the molecular role(s) of different immune cells using single cell RNA-sequencing. Preliminary data from this study are expected to pave the way for further investigations in larger clinical cohorts. The primary aim of this project will be to identify key inflammatory reduction biomarkers linked to MAPK-dependent alterations after CBD administration. Secondary outcomes include pain relief and reductions in pain-related symptoms. We will use a prospective pilot study design where patients will self-administer the investigational product (CBD-extract) for 60-days (2 months).

Specific Aim #1 – Determine the effects of CBD on chronic on quality of life in PLWH. We will compareQuality of Life (QoL) measures between treatment conditions, including pain and pain-related symptoms, if present.

Specific Aim #2 – Determine key biobehavioral mechanisms contributing to antiinflammatory and analgesic effects of CBD administration in PLWH. We hypothesize that change in molecular (alterations in cell signaling and reduction in inflammatory cytokines), psychological (reduction in pain-related fear and pain catastrophizing), and pain sensitivity regulation measures will be associated with pain relief, inflammation reduction, and reservoir shrinkage. We will quantify the shift in anti-inflammatory macrophage/monocyte population caused by CDB administration by examining gene expression at the single-cell level from the PBMC samples. This will allow us to accurately pinpoint gene under- or over-expression patterns at the RNA level (biomarkers), that are both induced by CBD administration in PLWH, and specific to different cells (e.g., monocytes, T cells, B cells, or other immune cells).

6. Research Plan

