Screening: Study coordinator will screen candidate to determine if they meet the inclusion criteria for the study. The baseline visit activity will be described to the patient. The patient will sign the consent form. Instruction/demonstration about CBD and dropper use will be provided.

Visit 1: Baseline Evaluation before CBD administration

Activities during visit 1:

- Patient reads and signs the consent form.
- Patient completes a brief form providing information (e.g. age, address, phone number, etc., health history).
- Measure of patient's height, weight, and vital signs (HR, blood pressure, body temperature).
- Patient completes a urine drug test
- Patient completes a urine pregnancy test is they have the ability to become pregnant
- Patient fills questionnaires: PASS (Pain Anxiety Symptom Scale; four dimensions of pain measured: cognitive anxiety, escape/avoidance, fearful appraisal, physiological anxiety), VAS (Pain Experience Visual Analogue Scales; anxiety, depression, anger), PSQI (Pittsburg Sleep Quality Index; self-report used to assess a subject's usual quality of sleep)
- A trained nurse or technician draws a blood sample
- The patient is given 2 30mL bottles with a syringe dropper with instructions/demonstration to take the solution under the tongue (0.5 cc ~1/2 dropper) twice per day (BID), 12 hours apart (morning and evening), at the prescribed daily dosage (62.5mg/day).
- The patient schedules the next test visits to the laboratory.
- The patient receives \$100 for completing this visit.

Visit 2: Follow-up after a month period of CBD administration

Activities during visit 2 (day 26-34):

- Measure vital signs of the patient as in visit 1.
- Questionnaire filling as in visit 1.
- Blood draw as in visit 1.
- The patient schedules the next test visits to the laboratory.
- The patient receives \$100 for completing this visit.

Visit 3: Follow-up after a two-month period of CBD administration

Activities during visit 3 (day 56-64):

- Measure vital signs of the patient as in visit 1.
- Questionnaire filling as in visit 1.
- Blood draw as in visit 1.
- The patient schedules the next test visits to the laboratory.
- The patient receives \$100 for completing this visit.

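### As worded, the regression of gene markers on inflammation does not target inflammation reduction, and the CRP, ESR and procalcitonin assays it needs are not scheduled

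*Combined protocol and SAP*

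**What the plan says.** **The regression.** Section 6, Primary Outcomes: "We will regress these gene markers against the variation in baseline inflammation (C-reactive protein, erythrocyte sedimentation rate, and procalcitonin"). The next line has no subject or main verb: "After CBD administration to obtain CBD-related biomarkers for inflammation reduction". No model, visit or change score is defined.

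**The aim.** Section 5: "The primary aim of this project will be to identify key inflammatory reduction biomarkers linked to MAPK-dependent alterations after CBD administration".

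**The expression contrast.** Section 6, CBD biomarker extraction: "We will contrast clusters of the same cell type at baseline (no CBD) and their counterparts after CBD administration". It is summarised by fold change, p-value and the fraction of cells expressing the gene. It uses no inflammation marker.

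**The samples.** The sampling paragraph of Section 6 states: "We plan to collect samples from five to seven patients over three time points: baseline (no CBD), and after one and two months of CBD-administration". That paragraph gives the samples one destination, single-cell RNA sequencing. Under Experimental Procedures, visit 1 has "A trained nurse or technician draws a blood sample" and visits 2 and 3 have "Blood draw as in visit 1". No blood assay is named at any visit. CRP, ESR and procalcitonin are named only under Primary Outcomes.

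**The concern.** This regression is the only step described that ties gene expression to a named measure of inflammation. The contrast under CBD biomarker extraction can show that expression changed. It cannot show that the change went with lower inflammation.

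A baseline marker is a single number per patient, fixed before the first dose. A gene associated with it marks who was more inflamed at entry, not who improved. If change was meant, the marker must also be measured after CBD, and the schedule does not provide for that. The documents describe no stored serum or plasma, so values missed at a visit cannot be assumed recoverable. A team that follows the text therefore ends with either a regression on the wrong target or no post-CBD marker data.

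**Working it through.** **1. The plan's own count.** 5 patients × 3 visits = 15 samples, and 15 × 5,000 = 75,000 cells. 7 × 3 = 21 samples, and 21 × 5,000 = 105,000 cells. Both agree with the plan. CRP, ESR and procalcitonin, however, give one value per patient per visit: 5 to 7 values at baseline, or 15 to 21 over three visits. The cell count adds nothing to this regressor.

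**2. The two readings.**

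| | Regressor is baseline | Regressor is change after CBD |
|---|---|---|
| Support in the text | The sentence as punctuated | The fragment after it, and the primary aim |
| Varies within a patient? | No | Yes |
| Targets inflammation reduction? | No | Yes |
| Assays needed | Visit 1 | Visits 1, 2 and 3 |
| Assays scheduled | None listed | None listed |

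**3. How well baseline stands in for change.** The plan gives no correlations, so these are assumptions: equal variances, and correlation ρ between baseline and follow-up. Then corr(baseline, change) = (ρ − 1)/√(2(1 − ρ)) = −√((1 − ρ)/2), and the share of variance explained is (1 − ρ)/2.
- ρ = 0.3: 35%
- ρ = 0.5: 25%
- ρ = 0.7: 15%
- ρ = 0.9: 5%

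Even this link arises only because the baseline is part of the change score.

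**4. Consequence for power.** Simulation with 20,000 replicates: one gene whose change correlates 0.9 (assumed) with the true change in inflammation, one marker, two-sided 0.05, ρ from 0.5 to 0.9.

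| | N = 5 | N = 7 |
|---|---|---|
| Baseline as regressor | 6 to 11% | 7 to 17% |
| Change as regressor | about 67% | about 90% |

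**5. Degrees of freedom.**
- One baseline marker: N − 2 = 3 or 5 residual df. The critical |r| at 0.05 is 0.878 (N=5) or 0.754 (N=7).
- All three markers together: N − 4 = 1 or 3.
- One marker over three visits, centred on each patient's own mean: 3N − N − 1 = 2N − 1 = 9 or 13.

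**6. Regression to the mean.** Let a gene correlate r with CRP within a visit, with visit-to-visit correlation ρ, cross-visit gene–CRP correlation rρ, and no CBD effect (all assumed). Then corr(gene change, baseline CRP) = −r√((1 − ρ)/2).
- r = 0.7, ρ = 0.5: −0.7 × √0.25 = −0.35
- r = 0.5, ρ = 0.7: −0.5 × √0.15 = −0.19
- r = 0.9, ρ = 0.3: −0.9 × √0.35 = −0.53

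The value −0.35 lies well inside the critical values in step 5. In simulation it reaches nominal 5% significance in about 8 to 9% of trials (N=5) and 11 to 12% (N=7).

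**7. What a within-patient slope shows.** In the same scenario with no CBD effect (r = 0.7, ρ = 0.5), corr(gene change, CRP change) = 2r(1 − ρ)/[2(1 − ρ)] = r = 0.70. The centred regression over three visits is significant in about 74% (N=5) and 87 to 88% (N=7) of simulated trials. It correctly finds a gene that tracks inflammation, but it is no evidence that CBD moved either one.

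**8. Screening limit.** Bonferroni over about 20,000 genes gives 0.05/20,000 = 0.0000025. With one change per patient, the critical |r| is then 0.9998 (N=5) or 0.9956 (N=7).

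**The case against.** The strongest reply is that a stray full stop caused the problem. Rejoined to the fragment, the sentence can mean variation from baseline after CBD. The primary aim and the before-and-after contrast both fit that reading. This stands. A reader might infer that the planned regression cannot identify markers of inflammation reduction, but the documents do not support so firm a claim. The favourable reading still leaves the model and visits undefined, and it makes the post-CBD assays indispensable.

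Second, the visit lists are not exhaustive. They also omit the Brief Pain Inventory and the SF-12, which the outcome text plans, and they do not name the sequencing either. This stands too. A reader might take the silence as proof that the markers were never to be measured. It shows only that the assays are unscheduled. Blood is drawn at all three visits.

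Third, the regression is one step within the primary outcomes. The expression contrast runs without it, so the whole primary analysis does not fail.

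Fourth, a reader might see regression to the mean as the main harm. Steps 5 and 6 show a modest inflation that rests on assumed correlations.

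Finally, a within-patient regression would flag many genes with no CBD effect (step 7). This is correct, and it limits what the repaired analysis may claim.

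**Conclusion.** The concern holds in this form: the regressor is undefined between baseline and change, its literal meaning misses the primary aim, and the reading that meets the aim needs assays that no visit lists. This goes beyond missing detail, because the post-CBD values must be obtained while the visits are taking place. It should be settled before the first patient's baseline visit.

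The textual finding needs no assumptions. Its size does: the contrast of 6 to 17% with 67 to 90% power assumes a true correlation of 0.9, ρ of 0.5 to 0.9, a single gene and two-sided 0.05, none of which the plan states. Those powers show the cost of using the wrong regressor. They do not suggest that the study is adequately powered once repaired.

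**What to change.** 1. List CRP, ESR and procalcitonin at visits 1, 2 and 3, from the draws already planned. Confirm blood volume and tube type, which the documents do not give.
2. Replace the sentence and the fragment with one pre-specified model. Summarise expression per patient, per visit and per cell type, starting with a pre-specified MAPK score. Regress it on one inflammation marker at a time, with both variables centred on the patient's own three-visit mean (9 to 13 residual df). Regressing change from visit 1 on change from visit 1 is a different estimator when there are three visits, so it should not be offered as an interchangeable option.
3. Report slopes with confidence intervals as exploratory. State that they show within-patient tracking with inflammation and not a CBD effect. Call a gene a candidate CBD-related marker of inflammation reduction only if it also changes in the baseline versus post-CBD contrast.

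The cost is a wording change and three routine assays on 15 to 21 samples. The fix corrects the target of the analysis. It does not make 5 to 7 patients enough for a screen of about 20,000 genes.
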